6.1. Enrolled Population

The Enrolled population will include all subjects who were randomized in Phase II of the INN-005 study, completed the Month 24 Visit of the INN-005 study, signed the Informed Consent Form for the INN-005-EXT study, and enrolled in the study. This will be the primary analysis population; all effectiveness and safety outcome measure analyses will be based on the Enrolled population.

6.2. Per-Protocol Population (PP)

The Per-Protocol (PP) population will include enrolled subjects who were randomized in Phase II of the INN-005 study excluding those that had any protocol deviations that would impact the effectiveness outcome measures.

The PP population will be used to analyze the secondary effectiveness outcome measures. InnFocus[ĀMNSĀNGĀQDFFĀL@PD@QĀ<FFĀHDHNDIFĀMĀ<HSĀMDĀMIĀNIĀNĀNĀRĀ from the PP. The PP population analysis will be conducted once all Month 60 visit data is collected.

Confidential Page 17 of 32

7. SUMMARY OF STUDY POPULATION DATA

7.1. Subject Disposition

Subject disposition will be summarized cumulatively for enrolled subjects by study group and overall. The summary will include the number and percentage (based on total number of subjects enrolled) of subjects in each of the following categories:

- Enrolled population
- Completed Month 36 Visit
- Discontinued prior to Month 36 Visit
- Completed Month 48 Visit
- Discontinued prior to Month 48 Visit
- Completed Month 60 Visit
- Discontinued prior to Month 60 Visit

A subject is considered to have discontinued the study if he/she withdraws participation or is withdrawn from the study by the Investigator, is deceased, or is Lost-to-Follow-up. The primary reason for exiting the study will also be provided.

7.3. Ocular Medical and Surgical History

For this study, the history includes ocular medical treatments, medication changes, any glaucoma reoperations, and surgical events for both the study and fellow eye occurring in the period between the completion of the last INN-005 visit (i.e., Month 24 Visit) and enrollment in the study. The history also includes adverse events (AEs) that occurred and resolved during this period.

For this study, medical and surgical history and adverse events will be mapped into a coded term by a Santen Clinical Scientist based on a review of all AE description records before the database lock.

The medical and surgical history will be summarized for the Enrolled Population. Subjects reporting any medical and surgical history at the Enrollment Visit will be tabulated by coded terms for each study group and overall.

7.4. Protocol Deviations

In this study, protocol deviations are categorized as follows:

- Assessment Not Performed Per Protocol
- Inclusion or Exclusion Criteria
- Informed Consent.
- Missed Assessment
- Missed Visit
- Out of Window Visit
- Other

A protocol deviation is considered *major* if it adversely affects the risk/benefit ratio of the study, the rights, safety, or welfare of the participants or others, or the integrity of the study. A protocol deviation that is not major is a *minor* protocol deviation. A *fellow eye protocol deviation* is one that only impacts the fellow eye.

InnFocus[ĀMNSĀN@ĀQDFFĀL@PĀ@QĀSHRĀPD<NDIHMĀ<HDĀNGĀMNĀĀJAĀprotocol deviations prior to database lock. All enrolled subjects with any major protocol deviation(s) will be tabulated by deviation category for each study group and overall. In addition, the following listings will be provided: (1) all major protocol deviations, (2) subjects excluded from the per

Confidential Page 19 of 32

protocol population (at Month 60 analysis), (3) all minor protocol deviations, and (4) fellow eye protocol deviations.

7.5. Concomitant Medications

For this study, a concomitant medication is defined as any non-glaucoma medication, like ocular medicine and supplements (including vitamins), taken during the study, at the time of consent, or within 30 days of consent. Medications that were administered more than 30 days prior to the consent to address an ongoing AE will also be considered as concomitant medication. Glaucoma medications in this study will not be considered as concomitant medications and will be analyzed separately. Concomitant medications will be mapped to preferred names in a similar manner as it was done in the INN-005 study.

Concomitant medications will be summarized for the Enrolled population. Subjects taking any concomitant medications will be tabulated by preferred drug name for each study group and overall. A subject will be counted at most once for each concomitant medication, even if the subject took the same concomitant medication on multiple occasions. In addition, concomitant medications will also be listed, separately.

Confidential Page 20 of 32

8. EFFECTIVENESS ANALYSES

8.1. Effectiveness-Related Definitions

8.1.1. Study Eye and Fellow Eye

The study eye of a subject is the eye that received either the PRESERFLO® MicroShunt with MMC or underwent trabeculectomy with MMC in the INN-005 study. Hence, the study eye in this study is the same as the study eye in the INN-005 study. The other eye is the non-study eye, or the fellow eye.

8.1.2. Screening Score

For any measure, the screening values are those that were obtained at the Screening Visit of the INN-005 clinical study. The terms screening and baseline are used interchangeably in the SAP.

8.1.3. Change (and Percent Change) from Screening

The change and the percent change from screening in a measure at a post-operative follow-up visit will be derived as:

- Change = (Score at the follow-up Visit) W(Screening Score)
- Percent Change from Screening = 100 × Change / (Screening Score)

8.1.4. Post-operative Interventions

At post-operative follow-up visits, interventions can be performed to assure a diffuse bleb and lower IOP. Interventions can be classified as either glaucoma medications or non-medication physical interventions.

8.1.4.2. Physical Interventions

8.1.4.2.1. Glaucoma Reoperations

Secondary surgical procedures which will be considered as failures of the INN-005 study original procedure include:

- 1. Trabeculectomy
- 2. Placement of a drainage device
- 3. Bleb revision (other than needling)
- 4. Explantation or repositioning of the PRESERFLO® MicroShunt
- 5. Iridectomy
- 6. Resuturing of the scleral flap
- 7. Glaucoma laser procedure (e.g., trabeculoplasty, iridotomy)
- 8. Other glaucoma surgery to reduce IOP

8.1.4.2.2. Other Glaucoma Procedures

Physical interventions will be performed to reduce the IOP, but will not be considered as failures of the INN-005 study original procedure, as follows:

- 1. XNeedling the blebYĀNPĀQIIG@ĀJLND<FĀGIIĀ@N@NĀNC@Ā=F@=
- 2. Needling with an injected antifibrotic
- 3. Laser removal of the blockage at the tip of the PRESERFLO® MicroShunt or at the Anterior Chamber entry point for a trabeculectomy

8.1.4.2.3. Other Post-Operative Intervention Procedures

Other post-operative intervention procedures that can be performed by the Investigator include:

- 1. Eye massage
- 2. Laser suture lysis in a trabeculectomy

8.1.4.3. Classification of Post-Operative Interventions

Qualifying glaucoma-related post-operative intervention includes glaucoma reoperations listed in Section 8.1.4.2.1, needling procedure and laser treatment listed in Section 8.1.4.2.2, use of a viscoelastic to limit aqueous flow, laser suture lysis in a trabeculectomy, and the introduction of any glaucoma medication. Eye massage will not be considered as a qualifying glaucoma-related post-operative intervention.

Confidential Page 22 of 32

8.1.5. Treatment Success and Failure

Total treatment success is defined as a subject with 20% or more reduction in IOP from the INN-005 study Screening to 60 months of post-operative follow-up without increasing the number of glaucoma medications.

Complete treatment success is defined as a subject with 20% or more reduction in IOP from the INN-005 study Screening without any glaucoma medication.

Qualified treatment success is defined as a subject with 20% or more reduction in IOP from the INN-005 study Screening with glaucoma medication supplement. The number of glaucoma medications should not exceed that at the INN-005 study Screening.

For this study, a *failure* is defined as a subject with one or more of the following:

- 1. No light perception vision confirmed on two consecutive study follow-up visits (i.e., two consecutive annual scheduled visits).
- 2. IOP persistently below 6mmHg (defined as an intraocular pressure below 6mm that is present on two consecutive scheduled/unscheduled visits).
- 3. Glaucoma Reoperations listed in Section 8.1.4.2.1.
- 4. Introduction of an oral carbonic anhydrase inhibitor.

The glaucoma needling procedures, listed in Section 8.1.4.2.2, and use of a viscoelastic to limit aqueous flow will be reported as *complications* but will not be considered failures, while other procedures, listed in Section 8.1.4.2.3, will not be considered as failures or complications.

8.2. Analyses of Primary Effectiveness Outcome Measure

There is no primary effectiveness outcome measure in this study.

8.3. Analysis of Secondary Effectiveness Outcome Measures

Unless specified otherwise, effectiveness analyses will be performed on the study eye, based on the Enrolled population, and summarized by study group. The analysis of the IOP secondary outcome measure will also be performed on IOP data, any of which will be censored (i.e., treated as missing) after a procedure or an event described in the definition of a failure in Section 8.1.4.3. Details on how to handle missing values are described in Section 5.2.1.

At each interim analysis, all effectiveness outcome measures will be summarized with descriptive statistics based only on observed cases.

8.3.2. Intraocular Pressure (IOP)

IOP data collected in both the INN-005 study and INN-005-EXT study on the Enrolled Population will be summarized descriptively by visits (INN-005 study Screening Visit and all postoperative follow-up visits). Subjects with any glaucoma reoperations will have their IOP data censored (i.e., treated as missing) and no imputation will be implemented. Change and percent change from the INN-005 study Screening in IOP will also be summarized for each study visit. In addition, the difference in mean percent change from Screening in IOP between study group and the corresponding 95% confidence intervals will be provided.

8.3.3. Qualifying Glaucoma-related Post-operative Interventions

The number and percentage of subjects with any qualifying glaucoma-related post-operative intervention by 36 months/48 months/60 months and the corresponding 95% confidence interval for such intervention rate will be calculated for each study group. Additionally, the rate difference and the corresponding 95% confidence interval of the rate difference will also be provided.

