9.3.4. Glaucoma Medications

A glaucoma medications assessment will be performed at the Enrollment Visit and documented on the appropriate CRF for the duration of the study. This assessment will include medications for both the study and fellow eye. Only glaucoma medications taken at the time of consent, and those taken within 30 days of consent, are required to be collected. If the action taken to address an ongoing AE was to administer glaucoma medication more than 30 days prior to consent, the medication should be recorded on the appropriate CRF. Each ocular hypotensive medication will be recorded on the CRF.

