5.2. Handling of Missing Data

5.2.1. Safety Outcome Measures

For both descriptive summaries and exploratory analyses of ECD measures and ECD response status, subjects in whom the anterior chamber is entered for non-MicroShunt related indications (e.g., reoperation with trabeculectomy, implantation of other glaucoma drainage device, iridotomy/iridectomy, cataract extraction), and subjects who had the entire MicroShunt explanted, will be censored (i.e., treated as missing) from analysis after the qualifying event. No imputation will be performed on missing or censored ECD data.

Descriptive summaries of other safety measures will be based on observed data only. No imputation of missing scores will be implemented.

Confidential Page 15 of 32

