9.2.2.5. Glaucoma Reoperation Due to Complication

For exploratory purposes, number and percentage of subjects with any glaucoma re-operation due to complication (not due to high IOP) by 36 months, 48 months and 60 months will be compared between study groups. Rate differences at those visits and their corresponding 95% confidence interval will be provided.

The data listing of subjects who experienced any glaucoma reoperation including the reason for glaucoma reoperation will be provided.

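### Cumulative intervention and reoperation rates by Months 36, 48 and 60 are planned as crude percentages, with no stated denominator or time origin and no allowance for early leavers

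*SAP*

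**What the plan says.** SAP 8.3.3 asks for the number and percentage of subjects with "any qualifying glaucoma-related post-operative intervention by 36 months/48 months/60 months", a 95% confidence interval per group, and the rate difference with its interval. SAP 9.2.2.5 states that the number and percentage with any glaucoma reoperation due to complication "by 36 months, 48 months and 60 months will be compared between study groups", again with rate differences and intervals.

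Neither section writes a denominator. The rules elsewhere in the SAP point in different directions:

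- SAP 6.1: "all effectiveness and safety outcome measure analyses will be based on the Enrolled population". SAP 8.3 repeats this default for effectiveness.
- SAP 8.3, for each interim analysis: "all effectiveness outcome measures will be summarized with descriptive statistics based only on observed cases".
- SAP 5.2.1, for safety measures other than endothelial cell density: "Descriptive summaries of other safety measures will be based on observed data only".

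The effectiveness missing-data rule (SAP 5.2.2) covers IOP and IOP response only. It does not address intervention status after a subject leaves. Protocol 9.6.5 bars data collection after withdrawal. No Kaplan-Meier, cumulative-incidence or person-time method appears in either document.

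The time origin is also open. SAP 4.2 sets Study Day 0 at the INN-005 surgery, but the Month 36 window for interventions in SAP Table 2 opens at Day 781.

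**The concern.** These are cumulative quantities over up to five years, in subjects whose follow-up can end early through withdrawal, death or loss. A plain percentage has to place each event-free leaver somewhere. Keeping such subjects in the denominator treats them as event-free to Month 60; removing them while keeping every observed event inflates the rate. The SAP does not choose, so even the direction of the bias depends on an unwritten programming decision.

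The proportion with a qualifying intervention is a named secondary effectiveness outcome, and the incidence of needling and reoperations is a named secondary safety outcome (Protocol 4.2). In a study whose purpose is long-term safety, the five-year rates and their arm difference are among the main results.

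**Working it through.** There is no planned figure to reproduce: the documents give no expected event rate and no dropout rate, overall or by arm. What follows is an illustration on assumed values.

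**Inputs (all assumed).** True event rate p = 30% over Months 24 to 60; dropout d = 10%, 20% or 30% over the same three years; constant hazards; dropout independent of events.

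**Formulas.** Three-year cumulative hazards are L = −ln(1 − p) and G = −ln(1 − d).

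- Observed events as a share of all enrolled: E = L/(L + G) × [1 − (1 − p)(1 − d)]
- Event-free completers: S = (1 − p)(1 − d)
- All-enrolled percentage: E
- Event-or-completed percentage: E/(E + S)

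**Case 1: all 30 points arise after Month 24.** L = 0.3567. At d = 10%, G = 0.1054, so E = 0.772 × 0.370 = 0.2856 and S = 0.630; then 0.2856/0.9156 = 0.312.

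| Dropout | All enrolled | Event-or-completed |
|---|---|---|
| 10% | 28.6% | 31.2% |
| 20% | 27.1% | 32.6% |
| 30% | 25.5% | 34.2% |

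With equal true rates and dropout of 10% versus 30%, the false arm difference is 28.6 − 25.5 = 3.1 points on the first denominator and 31.2 − 34.2 = −3.0 on the second. Equal dropout and equal true rates give none.

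For true rates of 10% to 40% on the all-enrolled denominator, understatement is 0.5 to 1.9 points at 10% dropout, 1.0 to 3.8 at 20%, and 1.6 to 5.9 at 30%. The false difference for 10% versus 30% dropout is 1.1 to 4.0 points.

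**Case 2: 20 of the 30 points arise before Month 24 (also assumed).** Everyone in the Enrolled population completed Month 24, so extension dropout cannot hide these events. Among the remaining 80%, the later rate is 10/80 = 12.5%, giving L = 0.1335. The all-enrolled percentage is 0.20 + 0.80 × E, with E computed at 12.5%: 29.5%, 29.0% and 28.4% at 10%, 20% and 30% dropout. The false difference for 10% versus 30% falls to about 1.1 points.

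This damping does not carry over to the other denominator. Early events all stay in, while event-free leavers drop out, so the percentages become 0.295/(0.295 + 0.630) = 31.9%, 0.290/(0.290 + 0.560) = 34.1% and 0.284/(0.284 + 0.490) = 36.7%.

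**Check of the remedy.** Simulating Case 1 with 200,000 subjects, Kaplan-Meier returned 30.1% at each of the three dropout levels, close to the true 30%.

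**The case against.** The strongest reply is that a reader might infer the rates are definitely understated because everyone enrolled is in the denominator. The documents do not establish that. SAP 6.1 and 8.3 name the analysis population; they do not say how leavers are counted, and the observed-case and observed-data rules permit a denominator under which the bias is upward. This stands, and it is why the point concerns an undefined estimator rather than a known downward bias.

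A reader might also infer that dropout will differ by arm. Unequal dropout is plausible in an open-label extension, where subjects may be told their treatment at consent (Protocol 8.1), but nothing in the documents shows it.

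Third, placing all events after Month 24 overstates the all-enrolled bias. Qualifying events include laser suture lysis and the introduction of any glaucoma medication (SAP 8.1.4.3), and early occurrence is likely for some of these. This also stands; Case 2 shows the reduction.

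Finally, the analyses are exploratory with no label claim (SAP 5 and 5.4), discontinuation before each visit is already tabulated by group (SAP 7.1), and Kaplan-Meier does not remove bias from informative dropout. All true. These points limit the consequence, but none supplies the missing denominator or accounts for unequal follow-up.

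**Conclusion.** The concern holds in this form: the two sections specify crude cumulative percentages without a denominator, a time origin or any allowance for early exit. The direction of the bias follows from the unwritten denominator. Its size cannot be derived from the documents. On the assumed values, a 30% rate is misread by about 1 to 4.5 points on either denominator when all events fall after Month 24. On the all-enrolled denominator the error is at most about 1.6 points when two thirds of the events are earlier. A false arm difference arises only if dropout differs by arm. These figures assume constant hazards and dropout unrelated to outcome.

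This should be corrected in the SAP. It does not touch the primary outcome and does not threaten a confirmatory claim.

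**What to change.** In SAP 8.3.3 and 9.2.2.5:

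- State the denominator, and state whether counting starts at the INN-005 surgery or at Day 781.
- Add Kaplan-Meier estimates, or cumulative incidence with death as a competing event, of time to first qualifying intervention and time to first reoperation. Report them at Months 36, 48 and 60 by arm, with 95% confidence intervals, the arm difference and numbers at risk. If time runs from surgery, say how delayed entry into the extension is handled.
- Keep the crude counts and show dropout by arm beside them.
- Take events between Month 24 and consent from the Reoperation Form and the medical/surgical history.

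One data question must be settled first. Protocol 9.3.3 asks for all medication changes since Month 24, whereas Protocol 9.3.4 says "Only glaucoma medications taken at the time of consent, and those taken within 30 days of consent, are required to be collected". Introduction of a glaucoma medication is a qualifying event, so the two sections need to be reconciled. If the dates prove incomplete, report the medication component separately.

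The cost is SAP text and standard code, with no new assessments, provided the gap-period medication dates are available. Intervals at Month 60 will be slightly wider, and the estimates still assume uninformative dropout.

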8.3.4. Glaucoma Medications

Glaucoma medications will be summarized descriptively by study group and study visits (Month 36, Month 48, and Month 60 visit). Number and percentage of subjects who are taking a given glaucoma medication will be provided for each study group at each study visit.

Number of glaucoma medication in use, change and percent change in number of glaucoma medications from the INN-005 study Screening will be summarized descriptively for each study group.

In addition to the glaucoma medication outcome measure, the following responder rates will also be summarized descriptively by study group and by study follow-up visits:

- Taking no glaucoma medications
- Having a V50% reduction in number of glaucoma medications from the INN-005 study Screening

Confidential Page 24 of 32

The number, percentage of responders and the 95% confidence interval for the responder rates will be calculated for each study group. Additionally, the rate differences and their corresponding 95% confidence intervals will also be provided.

8.3.5. Treatment Success

Proportion of study eyes considered a treatment success (total, complete, and qualified) will be summarized descriptively by study group and study visit. The number and percentage of subjects whose study eyes meet the treatment success criteria and the corresponding 95% confidence interval will be calculated for each study group. Additionally, the rate difference and the 95% confidence interval of the rate difference will also be provided.

8.4. Subgroup Analyses

Due to the small number of subjects who will enrolled in the INN-005-EXT study, no subgroup analysis is planned for this study.

Confidential Page 25 of 32

9. SAFETY ANALYSES

9.1. Safety-Related Definitions

9.1.1. Adverse Event

Under Protocol INN-005-EXT Section 12, an adverse event (AE) is any untoward medical occurrence, unintended disease or injury, or untoward clinical signs (including abnormal laboratory findings) in subjects, users or other persons, whether or not related to the investigational medical device or procedure. Any ocular AE that occurred prior to but is still ongoing at the time of consent or occur at any time after the date of informed consent through the last study visit will be collected for the INN-005-EXT study. Non-ocular serious adverse events (SAEs), whose definition is listed below, will also be collected; however, non-ocular non-serious adverse events will not be collected.

The severity of each AE will be graded by the Principal Investigator as Mild, Moderate, or Severe. AEs will also be rated by the Investigator as to their causality/relationship to the study procedure and to the study device.

Each AE will be mapped into a coded term by a Santen Clinical Scientist based on a review of all AE description records before the database lock.

9.1.1.1. Anticipated Adverse Event

Anticipated adverse events include those that might reasonably be expected to occur in this study because they are associated with glaucoma, glaucoma surgery, and/or prior cataract surgical procedures. A list of post-operative anticipated adverse events are available in section 13.1 and section 13.2 of the Clinical Investigation Plan (CIP) INN-005-EXT.

